#### 6.6.1.2 Unsolicited Adverse Events

Unsolicited AEs are defined as any spontaneously reported or discovered AE. Unsolicited AEs can also be solicited AE that leads to: A medically attended visit, an SAE, a discontinuation of study vaccine, a withdrawal from the study, or any solicited AE that persists beyond 7 days after the first study vaccine administration.

Unsolicited AEs will be coded using the MedDRA and displayed in tables using System/Organ/Class (SOC) and Preferred Term (PT). Treatment emergent AEs will be presented in tables, and all AEs will be included in listings where applicable.

In any tabulation, unsolicited AEs will be summarized by participant, therefore, a participant contributes only once to the count for a given Unsolicited AE (SOC or PT) in the tabulation. All episodes of all events will be provided in listings.

Unsolicited AEs with onset during the first 28 days after vaccination will be analyzed in the following analysis sets as defined below:

Analysis set	Timepoint
Phase 1/2/3a SAS	

After Dose 1, after Dose 2, after Dose 1 or 2

After Dose 3, after Dose 4

After Any dose

Phase 3b SAS	

After Dose 1, after Dose 2, after Dose 1 or 2

After Dose 3, after Dose 4

After Any dose

Phase 3c SAS	

After Dose 1, after Dose 2, after Dose 1 or 2

	• After Any dose
Pooled SAS	• After Dose 1, after Dose 2, after Dose 1 or 2
	• After Dose 3, after Dose 4
	• After Any dose

Participants will be considered for the computation of percentages in the specified time interval if they received the study vaccine in the specified interval. For each time interval the number of participants without missing dose will be presented.

Only data up to receipt of non-study COVID-19 vaccine (IcEv2) will be included in summary tables. Participant's data after the receipt of non-study COVID-19 vaccine will be summarized separately in a similar manner as unsolicited AEs for the following time interval: from the receipt of non-study COVID-19 vaccine up to the Final Visit/ET.

The following summaries will be presented for unsolicited AEs:

- Overview of number and percentage of participants with at least one:
  - AE
  - Related AE
  - AE by severity
  - MAAE
  - Related MAAE
  - SAE
  - Related SAE
  - AE leading to premature discontinuation of vaccine series
  - AE leading to withdrawal from study
  - AE with death as an outcome
  - AE with covid-related death as an outcome
- Number and percentage of participants with an AE by SOC and PT
- Number and percentage of participants with an AE by PT sorted by descending frequency in the ARCT-154 group
- Number and percentage of participants with an AE related to study vaccination by SOC and PT
- Number and percentage of participants with an AE by SOC, PT and severity
- Number and percentage of participants with an AE related to study vaccination by SOC, PT and severity

Overview tables and outputs by SOC and PT after each will be also produced by subgroups as specified in Section 6.2.5 based Phase 3b SAS.

Non-treatment emergent AEs will be listed.

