4.5.5 Additional Procedural Specifics

4.5.5.1 Diary Use to Collect Solicited Adverse Events

A Diary (electronic or paper if electronic is not feasible) will be used to collect solicited AEs (i.e., reactogenicity) directly from the participant:

- Solicited local and systemic AEs will be recorded daily for 7 days starting on the day of each study vaccination in the primary vaccination series (Day 1 and 29). For participants in Phase 2 and 3a, solicited AEs will also be recorded daily for 7 days following the 3rd injection (Day 92).
 - Solicited local AEs include injection site erythema, injection site pain, injection site induration/swelling, and injection site tenderness.
 - Solicited systemic AEs include arthralgia, chills, diarrhea, dizziness, fatigue, fever (categorized by measured body temperature), headache, myalgia, and nausea/vomiting.
 - Also solicited but not categorized as AEs are antipyretic and analgesic use.
 - All participants will be trained on what information will be collected from them following each vaccination. This includes how to evaluate and score each solicited AE. Some solicited AEs are not scored directly by the participant, but the values recorded will be analyzed for severity including body temperature and visible injection site reactions (erythema or induration/swelling). Body

temperature and visible injection site reactions will be measured daily by thermometer and ruler, respectively, provided by the site. Participants should be trained on how to use the thermometer (including capture of highest body temperature if the participant perceives the onset of possible fever) and the ruler. Participants should be encouraged to complete the diary at roughly the same time of day for the 7 days following vaccination when recording the solicited AEs.

- An electronic Diary (eDiary) will involve the use of an application on the individual participant's mobile phone or through the use of a loaner mobile phone with the application installed. If an eDiary is not feasible, then a paper diary will be used by the participant. Training on how to use either the electronic or paper diary will be performed at the time of the Day 1 visit. The eDiary will use prompts to encourage the participant to enter data, alerts to inform the site and other team members of potential toxicity grade solicited AEs (if relevant). Timely follow-up of these alerts is expected.

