4.5.5.4 Telephone Calls

Telephone calls will be performed at intervals specified in Section [4.5.3](#) and the schedule of assessments ([Appendix 1](#)) for the following reasons:

- To determine if any solicited AEs are persisting longer than 7 days after each study vaccination
- To evaluate for unsolicited AEs (including MAAEs, SAEs, AEs leading to discontinuation/withdrawal)
- To collect information for concomitant medication/vaccines
- To evaluate for symptoms of COVID-19 disease and risks of exposure to COVID-19. Solicitation of symptoms and risks of exposure to COVID-19 will follow a scripted interview provided in the Investigator Site File

Calls to the participant will be performed by a trained site team member designated by the investigator. However, in the event the participant reports any change in health status or change in medications, a qualified health care practitioner will need to complete the safety assessment.

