7.4.1.1 Definitions

7.4.1.1.1 Adverse Events

The investigator is responsible for reporting all AEs that are observed or reported during the study, regardless of their relationship to the study vaccine or their clinical significance. AE collection will begin after the signing of informed consent; however, AEs that occur prior to the administration of first dose of study vaccine (ie, non-treatment-emergent AEs) will be listed separately in the clinical study report.

An AE is defined as an untoward medical occurrence associated with the use of a medicinal product in humans, whether or not considered related to the medicinal product.

An AE can therefore be any of the following:

- Any unfavorable and unintended sign (including an abnormal laboratory finding), symptom, or disease temporally associated with the use of the study vaccine, whether or not considered related to the study vaccine
- Any new disease or exacerbation of an existing disease (a worsening in the character, frequency, or severity of a known condition)

- Recurrence of an intermittent medical condition (eg, headache) not present at baseline
- Any deterioration in a laboratory value or other clinical test (eg, electrocardiogram, X-ray) that is associated with symptoms or leads to discontinuation from the study vaccine

7.4.1.1.1.1 Solicited adverse events

The term “reactogenicity” refers to selected signs and symptoms (“reactions”) occurring in the hours and days following a vaccination. These signs and symptoms are collected as solicited AEs from participants by use of the Diary for 7 consecutive days following each of the first 2 study vaccine administrations.

- The following solicited AEs are included in the Diary:
 - **Solicited local AEs:** injection site erythema, injection site pain, injection site induration/swelling, and injection site tenderness
 - **Solicited systemic AEs:** arthralgia, chills, diarrhea, dizziness, fatigue, fever (categorized by measured body temperature), headache, myalgia, and nausea/vomiting

The occurrence of each of these solicited AEs is regarded as a vaccine-related AE.

Also solicited from participants but not categorized as an AE is the use of antipyretics and analgesics to prevent or treat solicited AEs.

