Solicited AEs are graded for severity according to scales defined in the Center for Biologics Evaluation and Research’s Guidance: Toxicity Grading Scale for Healthy Adult and Adolescent Volunteers Enrolled in Preventive Vaccine Clinical Trials ([DHHS 2007](#)), [Appendix 4](#).

Solicited AEs may also lead to circumstances that warrant collection of the events as unsolicited AEs. This includes any solicited AE that leads to:

- a medically attended visit
- an SAE
- a discontinuation of study vaccine
- a withdrawal from the study
- or any solicited AE that persists beyond 7 days after the first study vaccine administration.

Furthermore, should the site determine that the participant experienced and failed to enter a Grade 3 or Grade 4 solicited AE in the Diary during the time when the Diary was accepting data entry, this Grade 3 or Grade 4 solicited AE should be entered as an unsolicited AE in the CRFs.

7.4.1.1.1.2 Unsolicited adverse events

Unsolicited AEs are defined as any spontaneously reported or discovered AE.

Unsolicited AEs will be collected in all participants who receive at least 1 dose of study vaccine and are classified according to the following:

- mild, moderate, or severe
- whether or not the AE was categorized as an SAE, an MAAE, and/or an AE leading to discontinuation/withdrawal
- whether or not the AE was related to study vaccine or study procedure in the judgment of the investigator

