7.4.1.2 Eliciting and Documenting Adverse Events

AEs will be assessed from the time the participant signs the ICF until exit from the study. Any ongoing disease/condition (eg, intercurrent illness) that a participant is experiencing at the time of signing informed consent and during Screening should be captured as medical history.

Solicited AEs will be solicited by Diary for 7 days after each of the vaccinations in the initial series in all participants.

At every clinic visit and on weekly/monthly phone calls, participants will be asked a standard nonleading question to elicit any medically related changes in their well-being. Any and all new changes to the participant's health (including exacerbation of underlying disease) is regarded as an unsolicited AE.

In addition to participant observations, AEs identified from any study data (eg, physical examination findings, vital signs, or pulse oximetry) or identified from review of other documents (eg, participant Diary) that are relevant to participant safety will be documented on the AE page in the eCRF.

All solicited AEs through 7 days after each vaccination of the initial series will be collected. Continuing solicited AEs persisting beyond 7 days after each vaccination or that meet the

definition of a SAE or MAAE will be captured as unsolicited AEs, categorized accordingly and followed until stabilization/resolution.

All unsolicited AEs through 28 days after study vaccine administration will be collected.

Unsolicited AEs that meet the protocol definition of MAAE, SAE, or AEs leading to withdrawal/discontinuation will be captured for the duration of study participation.

If the investigator learns of any SAE, including a death, at any time after a participant has been discharged from the study, and he/she considers the event to be reasonably related to the study vaccine or study participation, the investigator must promptly notify the Sponsor.

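### SAP 6.6.1.2 and protocol 7.4.1.1.1.1 tie the 7-day persistence rule for solicited reactions to the first dose, protocol 7.4.1.2 ties it to each dose, and nothing reconciles them.

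*SAP*

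**What the plan says.** SAP 6.6.1.2 defines unsolicited AEs as spontaneously reported or discovered events and then widens the definition: "Unsolicited AEs can also be solicited AE that leads to: A medically attended visit, an SAE, a discontinuation of study vaccine". Study withdrawal follows in the list, and the last item is "any solicited AE that persists beyond 7 days after the first study vaccine administration".

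Protocol 7.4.1.1.1.1 gives a matching list that ends "or any solicited AE that persists beyond 7 days after the first study vaccine administration". It adds that if a severe reaction should have been entered in the diary but was not, "this Grade 3 or Grade 4 solicited AE should be entered as an unsolicited AE in the CRFs".

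Protocol 7.4.1.2, the section on eliciting and documenting AEs, states a different rule. There, "Continuing solicited AEs persisting beyond 7 days after each vaccination" are to be captured as unsolicited AEs and followed. Protocol 4.5.5.4 gives as a purpose of the calls: "To determine if any solicited AEs are persisting longer than 7 days after each study vaccination".

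Diary collection is short. Protocol 7.4.1.1.1.1 describes use of the "Diary for 7 consecutive days following each of the first 2 study vaccine administrations". Protocol 4.5.5.1 adds a 7-day diary after the Day 92 injection in Phase 2 and 3a. SAP Section 7, which lists changes from the protocol including several to the safety estimands, does not mention the persistence rule.

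**The concern.** The diary closes after 7 days, so the AE page is where a longer reaction would show. Unsolicited AEs within 28 days of each dose are part of the primary safety objective, and SAP 6.6.1.2 tabulates them by dose. Under a rule limited to the first dose, a long reaction after dose 1 would enter the unsolicited AE tables, while the same reaction after dose 2 or the Day 92 dose might not. A difference between doses could then reflect the recording rule. Sites working from different protocol sections could also collect different data. Solicited AEs count as vaccine-related by definition, so anything missing would be a related event.

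**Working it through.** The plan states no figure for this point, so the check sets the texts side by side and follows one case through them.

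| Place | Persistence rule applies after |
|---|---|
| Protocol 7.4.1.1.1.1 (definition) | first vaccination |
| SAP 6.6.1.2 (definition for analysis) | first vaccination |
| Protocol 7.4.1.2 (eliciting and documenting) | each vaccination |
| Protocol 4.5.5.4 (call purposes) | each vaccination |

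Protocol 4.5.3.6 sides with the last two. It requires the calls on Days 8, 36, 99 and 127 to fall at least 7 days after the preceding dose, so that solicited events are adequately recorded.

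**Case: injection-site pain starts on the day after dose 2 and lasts 10 days, with no medical visit.**

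1. *Diary data.* It is counted and graded in the after-dose-2 reactogenicity tables under either rule. The endpoint is a solicited AE starting within 7 days, so duration does not enter.
2. *Unsolicited AE data, each-dose rule.* It is recorded on the AE page. Whether onset is dated to the start of the reaction or to day 8, it falls within 28 days of dose 2 and enters that table.
3. *Unsolicited AE data, first-dose rule.* The persistence criterion does not apply. The listed routes left are medical attendance, SAE, discontinuation and withdrawal, plus an unentered Grade 3 or 4 event under the protocol. None fits, so the persistence may go unrecorded.

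**Which reactions have another route after dose 2.** Protocol 4.5.3.7 asks for COVID-19 testing when fever or chills, fatigue, muscle or body aches, headache, nausea or vomiting, or diarrhea persist beyond 7 days after vaccination. Under 7.4.1.1.4, an AE leading to an unscheduled visit, including one for possible COVID-19 symptoms, is an MAAE and goes on the AE page. The diary has 4 local and 9 systemic terms. Of the systemic terms, 7 are covered this way (fever, chills, fatigue, myalgia, headache, nausea/vomiting, diarrhea). That leaves 9 − 7 = 2 (arthralgia, unless read as a body ache, and dizziness) and the 4 local terms. The route is weaker after the Day 92 dose, because swabs are no longer required after Day 92 in Phases 1, 2, 3a and 3b.

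**Planned ARCT-154 doses to which the discrepancy applies** (protocol 4.1 and 4.5.2):

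- Second doses of the initial series: 750 (Phase 1/2/3a: 75 + 225 + 450) + 8,000 (3b) + 1,200 (3c) = 9,950.
- Day 92 diary doses in Phase 2/3a: (225 + 450) × 3/4 = 675 × 0.75 ≈ 506 third doses, plus 75 + 150 = 225 participants switching from placebo; 506 + 225 = 731.

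For the 225 who switch, the first study injection was placebo. A literal first-dose rule would skip their first exposure to ARCT-154.

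These are counts of doses, not of reactions lost. The documents give no rate of reactions beyond 7 days by which to multiply them.

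**The case against.** The strongest reply is that this is a slip in one list item, without effect on the data. The sections that direct collection say each vaccination, the calls ask about it, and protocol 7.4.1.3 has all AEs followed to resolution. Both definitions are open-ended, so a persistent reaction found on a call could qualify simply as a discovered AE. The SAP specifies no filter that removes AE records by dose. Long reactions may also be few: protocol 2.6 says most ARCT-021 solicited events were no longer reported by the end of 7 days, and 4.5.3.7 says ARCT-154 symptoms have typically resolved or improved by then. Finally, rewording the protocol cannot change what was collected. The SAP is dated 20 July 2023, and by 12 January 2023 all Phase 1/2/3a/3b participants had at least 6 months of follow-up after the second vaccination or had terminated early.

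Most of this stands, and it limits the consequences. It does not settle which rule sites applied, and neither document says.

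A reader might infer more than the texts support:

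- *Such reactions vanish from both datasets.* They do not; the first 7 days remain in the diary tables.
- *The primary reactogenicity endpoint is under-counted.* It depends on onset, so it is unaffected.
- *Dose 1 and dose 2 rates are not comparable.* That presumes a divergence in site practice that nothing in the documents shows.
- *Some 9,950 or 731 events are at stake.* Those figures count doses under the rule.

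**Conclusion.** The contradiction is real and unreconciled. As written, the SAP's persistence criterion leaves out prolonged reactions after dose 2 and after the Day 92 diary dose in Phase 2/3a, contrary to protocol 7.4.1.2.

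The consequence is conditional and narrow. If the first-dose wording was applied at sites or in programming, the tail beyond day 7 can be absent from the unsolicited AE data for reactions that met no other criterion. After dose 2 these are chiefly local reactions, dizziness and perhaps arthralgia, provided the COVID-19 evaluation in 4.5.3.7 was carried out as described. After Day 92 the set is wider. How many events this involves cannot be estimated from the documents. The point warrants correction before lock but gives no ground for calling the primary safety results biased.

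**What to change.** In SAP 6.6.1.2, change the persistence item so that it refers to each study vaccine administration rather than the first, consistent with protocol 7.4.1.2. Add an entry in SAP Section 7 recording the conflict with protocol 7.4.1.1.1.1 and how it was resolved.

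Before lock, run a programmed check of diary data against AE records. List every reaction still ongoing on the last diary day after the Day 29 dose, and after the Day 92 dose in Phase 2/3a, that has no matching AE record. State in the study report which rule the collected data followed. The same listing for dose 1 would show whether matching differs by dose.

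The cost is one phrase, one Section 7 entry and one programmed listing. Site queries this late may resolve only some records, so the listing should be reported even where queries fail.

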8.7.7 Other Analyses

Summary statistical analyses will be provided for demographics, medical history, physical examination, social history, and risk factor variables at baseline, as well as vital signs, clinical laboratory tests, etc.

8.7.8 Analyses of Immunogenicity, Safety and Efficacy Data Post Day 92 (Phase 1/2/3a, Phase 3b and Pooled Cohorts)

Participants in Phase 1/2/3a and Phase 3b receive additional study drug (after the initial two-dose vaccination series) at Day 92 (Section 4.5.2). Immunogenicity data before and after Day 92 will be presented separately for these participants.

All safety data collected post Day 92 will be presented separately, using the same methods described in Estimand 2 or 3. Safety data collected post Day 92 include solicited AEs (Phase 2/3a participants only), unsolicited AEs, MAAEs, AEs leading to discontinuation/withdrawal, and SAEs.

Efficacy data after Day 92 will only be collected for Phase 3c participants and will be presented up to Day 394. Rate and 95% CI of the confirmed infection will be calculated using Poisson distribution.

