- l Review of AEs will include surveillance for solicited (only after Day 92 vaccination and only for Phase 2 and 3a) and unsolicited AEs, SAEs, MAAEs, and AEs leading to discontinuation/withdrawal; Solicited AE data will be gathered by Diary for Day 1 through Day 7 for all participants after each of the initial vaccination series only; Unsolicited AE data will be gathered by interview at clinic visits and telephone contacts through Screening and 28 days after each vaccination. SAEs, MAAEs, and AEs leading to discontinuation/withdrawal will be collected at all timepoints after signing of the informed consent.
- m Only participants in Phase 2 and 3a complete a diary after vaccination on Day 92; no diary is completed after vaccination on Day 120. Participants in Phase 1 and 3b do not complete a diary after vaccination on either Day 92 or Day 120.
- n For participants in Phase 1 and Phase 3b, the visit window at Day 92 is +30 days. For participants in Phase 2 and Phase 3a, the visit window at Day 92 is +14 days.

- o Participants ineligible for additional doses (Section 5.1.5) do not have a clinic visit at Day 120 and will not have weekly telephone visits on Day 99 to Day 113 and Days 127 to Day 176 but will have monthly telephone visits instead on Days 120, 150, and 180.

DAY 92 TO END OF STUDY VISIT FOR PHASE 3C PARTICIPANTS

Visit Name	Weekly Study Call	Follow-up Visit	Weekly Study Call	Monthly Study Call	Final Visit	Unscheduled Visit ^b	ET Visit
Visit Type ^a	TC	Clinic	TC	TC	Clinic	Clinic	Clinic
Study Day:	92, 99, 106, 113, 120, 127, 134, 141, 148, 155, 162, 169, 176, 183, 190, 197, 204	211	218, 225, 232, 239, 246, 253, 260	290, 320, 350	394	N/A	N/A
Visit Window (days):	± 2	+30	± 2	± 2	+14	N/A	N/A
Physical examination ^c		X			X	X	X
Vital signs and body temperature ^d		X			X	X	X
Pulse oximetry						X	
Blood sampling ^e		X			X		X
Nasal swab sample for RT-PCR SARS-CoV-2 ^f						X	
Review of Medical History		X			X	X	X
Review for COVID-19 symptoms and risks ^g	X	X	X	X	X	X	X
Adverse events ^h	X	X	X	X	X	X	X
Concomitant medication/vaccines collection	X	X	X	X	X	X	X

Abbreviations: AE=adverse event; COVID-19=coronavirus disease 2019; ET=early termination; MAAE=medically attended adverse event; N/A=not applicable; RT-PCR=reverse transcription polymerase chain reaction; SAE=serious adverse event; SARS-CoV-2=severe acute respiratory syndrome coronavirus 2; TC=telephone call

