- **Safety Analysis Set (SAS):** Includes all participants who receive any dose of study vaccine (ARCT-154 or placebo or ChAdOx1). Participants will be analyzed according to the study vaccine received. SAS analysis sets are defined for each Phase of the study as follows:
  - Phase 1/2/3a SAS: this pools data from Phase 1, Phase 2 and Phase 3a participants
  - Phase 3b SAS
  - Phase 3c SAS
  - Pooled SAS: this pools data from Phase 1/2/3a/3b for ARCT-154 and placebo, respectively. It will include evaluations up to Day 92 only (except for unsolicited events)
- **Reactogenicity Analysis Set (RAS):** Includes all participants who receive any dose of study vaccine (ARCT-154 or placebo or ChAdOx1) and provide at least 1 reactogenicity diary report. Participants will be analyzed according to the vaccine received.  
Reactogenicity analysis sets are defined for each Phase of the study as follows:
  - Phase 1/2/3a RAS: this pools data from Phase 1, Phase 2 and Phase 3a participants
  - Phase 2/3a RAS
  - Phase 3b RAS
  - Phase 3c RAS
  - Pooled RAS: this pools data from Phase 1/2/3a/3b for ARCT-154 and placebo, respectively.

For safety analysis sets, SAS and RAS, where participants will be analyzed according to the study vaccine received, in case a participant receives incorrect study vaccine, only data up to the receipt of the incorrect study vaccine (exclusive) will be used in the summaries. If the first dose of vaccine the participant received was the incorrectly assigned one, then only data up to the second dose (exclusive) will be used in the summaries. Outputs for “any dose” that analyze data after any ARCT-154 dose or after any Placebo or ChAdOx1 dose, will include all data after each dose even if participant received an incorrect study vaccine.

Separate listings of safety and immunogenicity data, that are currently planned in this SAP, will be produced for participants receiving at least one incorrect dose of study vaccine. Of note, participants with missing dosing will not be considered as receiving incorrect dosing.

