#### Phase 1/2/3a, Phase 2/3a, Pooled:

Since participants underwent Switchover at Day 92 or were re-randomized (participants initially randomized to ARCT-154 in Phase 2 and 3a) at Day 92 and then received Placebo at Day 120, headers by dose will be presented in the following way:

- Baseline and disposition outputs:

ARCT-154 (Initial)	Placebo (Initial)	Total
--------------------	-------------------	-------

- Analysis of data up to the Switchover/Further study vaccine:

ARCT-154 (Initial)	Placebo (Initial)
--------------------	-------------------

- Analysis of data after Switchover/Further study vaccine

ARCT-154 (Initial)	Placebo (Initial)	
ARCT-154 (Dose 3)/ Placebo (Dose 4)	Placebo (Dose 3 and 4)	ARCT-154 (Dose 3 and 4)

- Analysis of combined data before and after Switchover/Further study vaccine:

ARCT-154 (Initial)	Placebo (Initial)		
ARCT-154 (Dose 3)/	Placebo	Not Re-randomized	ARCT-154

Placebo (Dose 4)	(Dose 3 and 4)	(Dose 3 and 4)
------------------	----------------	----------------

- Analysis of data over multiple doses

ARCT-154 vaccine at any time; no ARCT-154 vaccine:

ARCT-154	Placebo
----------	---------

- Analysis of data from the first dose of ARCT-154 vaccine administration:

ARCT-154
----------

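### The pooled After Dose 3 table of unsolicited AEs mixes diary and non-diary participants: about 100%, 2.0% and 2.7% of its three columns are assigned a diary

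*SAP*

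**What the plan says.** **Diary.** Protocol Appendix 1 (Day 92 to end of study, Phases 1 to 3b) gives the rule in a footnote: "Only participants in Phase 2 and 3a complete a diary after vaccination on Day 92; no diary is completed after vaccination on Day 120". It adds: "Participants in Phase 1 and 3b do not complete a diary after vaccination on either Day 92 or Day 120". Protocol Section 8.7.8 agrees: "Safety data collected post Day 92 include solicited AEs (Phase 2/3a participants only), unsolicited AEs, MAAEs". SAP Table 8 likewise shows solicited events after Day 92 for the Phase 2/3a RAS only.

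**Classification.** SAP Section 6.6.1.2: "Unsolicited AEs are defined as any spontaneously reported or discovered AE". Under Protocol Section 7.4.1.2, health changes elicited at visits and calls count as unsolicited AEs. Diary reactions are solicited, with exceptions. Protocol Section 7.4.1.1.1.1 says: "Solicited AEs may also lead to circumstances that warrant collection of the events as unsolicited AEs". The listed cases are a medically attended visit, an SAE, discontinuation or withdrawal, and persistence beyond 7 days. A Grade 3 or 4 reaction missed in the diary is also entered as unsolicited.

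**Tables.** SAP Section 6.6.1.2 says: "Unsolicited AEs with onset during the first 28 days after vaccination will be analyzed in the following analysis sets as defined below". It plans 28-day unsolicited AE tables after Dose 3, after Dose 4 and after any dose for the Phase 1/2/3a, Phase 3b and Pooled SAS. The columns come from SAP Section 5.3.1, under "Analysis of data after Switchover/Further study vaccine". There are three: initial ARCT-154 then ARCT-154 at Dose 3; initial ARCT-154 then placebo; and initial placebo then ARCT-154.

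**Reach of the Pooled SAS.** Protocol Section 8.2 stops the Pooled SAS at Day 92. SAP Section 4.1 adds an exception: "It will include evaluations up to Day 92 only (except for unsolicited events"). The change tables in SAP Section 7 do not list it.

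**The concern.** The same reaction to the same vaccine is filed differently according to study phase, and at Dose 3 phase is almost the same thing as column. The third-dose ARCT-154 column consists entirely of Phase 2/3a participants, whose short-lived reactions go mostly to the diary and the RAS tables. The other two columns are almost entirely Phase 3b, where a reported reaction can only be an unsolicited AE. Someone comparing rates across the pooled table would be comparing collection methods as well as vaccines.

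A cleaner comparison exists. Within Phase 2/3a, a third ARCT-154 dose versus placebo at Day 92 is a randomized 3:1 contrast with a diary in both arms. Pooling replaces that placebo arm with a column about 98% of which has no diary. No Phase 2/3a-only unsolicited AE table is planned. SAP Section 7.1 drops the separate display of Phase 1 and Phase 2/3a safety on the ground of common entry criteria, without considering the diary.

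**Working it through.** **Inputs.** Planned arm sizes (Protocol Section 4.1), ARCT-154:placebo: Phase 1, 75:25; Phase 2, 225:75; Phase 3a, 450:150; Phase 3b, 8,000:8,000. At Day 92 (SAP Section 2.1), Phase 2/3a initial ARCT-154 recipients are re-randomized 3:1 to ARCT-154 or placebo. Phase 1/3b initial ARCT-154 recipients go to placebo, and all initial placebo recipients go to ARCT-154.

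**The plan's own figure.** 75 + 225 + 450 = 750 on ARCT-154, matching the approximately 750 in SAP Section 6.1. Placebo is 25 + 75 + 150 = 250. The documents give no diary-coverage figure.

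**Coverage.** Phase 2/3a participants in the column divided by everyone in the column, assuming all randomized participants receive Dose 3. Phase 2/3a has 225 + 450 = 675 on initial ARCT-154 and 75 + 150 = 225 on initial placebo.

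| Column after Dose 3 | Phase 2/3a (diary) | Pooled column | Pooled coverage | Phase 1/2/3a SAS coverage |
|---|---|---|---|---|
| ARCT-154 then ARCT-154 | 0.75 × 675 = 506 | 506 | 100% | 100% |
| ARCT-154 then placebo | 0.25 × 675 = 169 | 169 + 75 + 8,000 = 8,244 | 2.05% | 169/244 = 69% |
| Placebo then ARCT-154 | 225 | 225 + 25 + 8,000 = 8,250 | 2.73% | 225/250 = 90% |

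**Sensitivity to Dose 3 uptake (assumed).** If 75%, 50% or 25% of Phase 3b receives Dose 3 and the other phases are fully retained, the second column has 2.7%, 4.0% or 7.5% coverage and the third 3.6%, 5.3% or 10.0%. The first stays at 100%.

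**What this could do to a rate (illustration only).** Suppose a share r of every column would report a short-lived listed reaction, and diary participants contribute none of these to the unsolicited table. The collection method alone then adds r × (1 − coverage):

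- r = 5%: 0%, 4.9% and 4.9% in the three columns.
- r = 10%: 0%, 9.8% and 9.7%.
- r = 20%: 0%, 19.6% and 19.5%.

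The documents give no value for r. A common r is used only to isolate the effect of collection.

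**Dose 4 and Phase 3b.** After Dose 4 no column has a diary. In the Phase 3b SAS table after Dose 3, neither arm has one. Both tables are uniform across columns. Reading Phase 3b by dose is another matter: doses 1 and 2 have a diary and doses 3 and 4 do not, and the after-any-dose table combines them.

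**The case against.** The strongest reply is that this is one descriptive table of limited standing, and most of that is right. The overall primary safety endpoints are those in the Phase 3b SAS and RAS. Pooled endpoints are sensitivity analyses (SAP Section 6.2.4), and SAP Table 4 confines pooled safety to Day 92. Safety analyses after the primary one are exploratory (Protocol Section 8.9.2). There is no safety hypothesis test, and SAP Section 7.2 removes confidence intervals from AE rates. Third-dose reactions are not hidden either: the Phase 2/3a RAS tables show them overall, by grade and by day, and the SOC and PT listings would reveal reaction-type terms. These facts limit the consequence, but they do not make the three columns comparable.

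The classification step is inferred from definitions rather than stated in one sentence, and some wording is loose. Protocol Section 4.5.3.6 times the Day 99 and Day 127 calls so that solicited events are recorded, without naming phases. Protocol Section 4.5.3.2 says diaries are not used after Switchover vaccinations. If that applied to Phase 2/3a placebo recipients, the third column would fall from 2.7% to 0% and the imbalance would remain. The Appendix 1 footnotes settle the matter for Phase 1 and 3b.

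The diary asymmetry is protocol design, so Section 7 need not list it. The Day 92 exception for the Pooled SAS is a different matter. The title of Protocol Section 8.7.8 does name pooled cohorts after Day 92, but Section 8.2 ends the Pooled SAS there, and the SAP's exception goes unremarked. A row in SAP Section 7.2 mentions a Phase 2/3a SAS, but Sections 4.1 and 6.6.1.2 contain none.

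**Conclusion.** The point holds for the pooled After Dose 3 unsolicited AE table, where diary assignment is about 100%, 2.0% and 2.7%. It holds in a milder form for the Phase 1/2/3a SAS table (100%, 69%, 90%). These figures rest on planned sizes and on everyone receiving Dose 3, and they count diaries assigned, not completed. The imbalance survives a fall in Phase 3b uptake to 25%.

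Stronger readings are tempting but not supported:

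- **That the third dose will look safer than first-course ARCT-154, or close to placebo.** The direction is plausible for short-lived events, but the size depends on spontaneous reporting rates that the documents do not give. The solicited AE rate above 90% in Protocol Section 2.6 concerns ARCT-021, a different vaccine.
- **That Phase 3b rates will rise after doses 3 and 4 purely from the recording change.** They might; this also depends on reporting.
- **That Phase 2/3a reactions never enter the unsolicited data.** Escalated, persistent and missed Grade 3 or 4 events do.
- **That the After Dose 4 columns are distorted.** Nobody has a diary then.
- **That the primary safety conclusion or type I error is at risk.** The table lies outside the overall primary endpoints and is not tested.

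**What to change.** In SAP Section 6.6.1.2:

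1. Replace the Pooled SAS After Dose 3 unsolicited AE table with separate Phase 2/3a and Phase 1/3b tables, so that the randomized third-dose contrast has uniform collection. This needs the Phase 2/3a SAS of Protocol Section 8.2 restored in SAP Section 4.1.
2. For doses without a diary, give the unsolicited AE total with and without solicited-type terms starting within 7 days. Take the terms directly from the list in Protocol Section 7.4.1.1.1.1, so that nothing is chosen from the data.
3. Footnote that by-dose and after-any-dose rates mix diary and non-diary doses, and that the Phase 1/2/3a After Dose 3 columns differ in diary coverage.
4. Keep the After Dose 4 table, with a footnote that no participant had a diary.

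List the Day 92 exception for the Pooled SAS in SAP Section 7, and reconcile it with SAP Table 4.

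The cost is one pooled table lost, a few rows and footnotes added, and modest programming. No new data are required.
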